#### **Primary estimand**

#### **United States registration**

The primary clinical question of interest is

What is the treatment difference between LY3209590 and insulin glargine in HbA1c change from baseline to Week 52, in study eligible participants, regardless of treatment discontinuation for any reason and regardless of initiation of rescue medication?

#### Treatment regimen estimand attributes

This table describes the treatment regimen estimand attributes.

Treatment Regimen Estimand Attribute	Description
Population	Targeted study population. See Section 9.2 for details.
Endpoint	HbA1c change from baseline to Week 52.
Remaining intercurrent events	None. The 2 intercurrent events, treatment discontinuation for any reason and initiation of rescue medication, are both addressed by the treatment condition of interest attribute.
Treatment condition	The randomized treatment regardless of treatment discontinuation and use of rescue medications.
Population-level summary	Difference in mean changes between treatment conditions.

#### Rationale for the treatment regimen estimand

The treatment regimen estimand estimates how participants with T2D are treated in clinical practice and considers both efficacy and safety.

## Registration for countries outside the United States

The primary clinical question of interest is

What is the treatment difference between LY3209590 and insulin glargine in HbA1c change from baseline to Week 52, in study eligible participants who adhere to the randomized treatment without intercurrent events during the study treatment period?

#### Efficacy estimand attributes

This table describes the efficacy estimand attributes.

Efficacy Regimen Estimand Attribute	Description	
Population	Targeted study population. See Section 9.2 for details.	
Endpoint	HbA1c change from baseline to Week 52.	
Remaining intercurrent events	None. The 2 intercurrent events, treatment	
	discontinuation for any reason and initiation of rescue	
	medication, are both handled by the hypothetical	
	strategy, for example, the potential outcome for those	
	participants if the intercurrent events have not occurred	
	will be estimated.	
Treatment condition	The randomized treatment.	
Population-level summary	Difference in mean changes between treatment	
	conditions.	

#### Rationale for the efficacy estimand

The efficacy estimand supports the interpretation of the treatment effect as participants adhere to study treatment and free from the confounding effect of rescue medications.

#### Secondary estimand for gated objective

The superiority test in change from baseline to Visit 33 (Week 52) in HbA1c will also be based on the primary estimands described above.

## 4. Study Design

## 4.1. Overall Design

This is a Phase 3, parallel-design, open-label, randomized control study to evaluate the efficacy and safety of LY3209590 administered once-weekly compared to insulin glargine administered daily in adult participants with T2D that are insulin naïve.

The study includes a 3-week screening and lead-in period, a 52-week treatment period, and a 5-week safety follow-up period after the last visit in the treatment period.

Participants will be randomly assigned to receive daily insulin glargine or weekly insulin LY3209590.

#### Participants randomly assigned to insulin glargine

Participants randomly assigned to insulin glargine will start on 10 U/day and will have weekly dose adjustments based on FBG and hypoglycemia events (see Section 6.5.2).

#### Participants randomly assigned to receive LY3209590

Participants randomly assigned to receive LY3209590 will be on a fixed dose escalation for at least the first 16 weeks of the study. Participants will start LY3209590 on a fixed dose of 100 U per week and will escalate the LY3209590 dose every 4 weeks as required to the set doses of 150, 250, and 400 U per week. Treat-to-target dose adjustments will be based on FBG of 80 to 130 mg/dL (4.4-7.2 mmol/L) and hypoglycemia events (see Section 6.5).

Dose administration will be via a fixed dose autoinjector.

After Week 16, if a participant who has received the fixed dose of 400 U per week for at least 4 weeks has median FBG levels >130 mg/dL, then the investigator should transition the participant to titratable doses using a prefilled pen. This will provide more dosing flexibility and allow dose titrations above 400 U per week.

If a participant transitions from the fixed dose autoinjector to a prefilled pen, they must continue using the prefilled pen for the remainder of the study.

#### Screening and Lead-In

#### Screening

Interested participants will sign the appropriate informed consent document(s) prior to initiating any procedures.

The investigator will review medical history, symptoms, risk factors, and other inclusion and exclusion criteria prior to any diagnostic procedures. If the participant is eligible after this review, then the site will perform the diagnostic procedures to confirm eligibility.

#### Lead-In

Participants will receive their glucometer and electronic study diary and receive training on

- diabetes self-monitoring and management
- electronic study diaries, and
- study requirements.

Starting with Visit 2, participants must measure their FBG levels each day when possible or at a minimum 3 times per week.

Participants will continue their current diabetes therapy until randomization.

## **Treatment period**

#### Weeks 0-16 (Visits 3-18)

This is the general flow for Visit 3

- study personnel confirm enrollment criteria
- participants are randomly assigned to an intervention group
- study personnel complete baseline procedures and sample collection
- study personnel will provide dosing training and the participant receives the first dose of LY3209590 or insulin glargine, and
- study personnel complete all visit procedures.

Participants assigned to LY3209590 will receive the fixed weekly dose delivered by an autoinjector, and participants assigned to insulin glargine will use daily titratable doses delivered by prefilled pen. Weeks 0-15 cover the first 16 doses for those assigned to LY3209590.

See Section 6.5 for detailed dosing information for LY3209590 and insulin glargine.

Week 1 (Visits 4 and 5)

Visit 4 – telehealth visit

Study personnel should review FBG and hypoglycemia events from the previous week to confirm the appropriate dose.

For participants assigned to LY3209590, study personnel will confirm the participant administers their second dose on that day and the timing of their second dose.

Participants should record the date and time of the second dose in the e-diary.

Study personnel will schedule Visit 5,  $3(\pm 1)$  days after Visit 4 (and the second dose of LY3209590 or daily dose of insulin glargine) in order to collect a PK sample at the appropriate time. A sample will be collected for participants on LY3209590 and insulin glargine.

Visit 5 – on-site clinic visit. Note: Visit 5 and Visit 6 cannot be scheduled on the same day.

Study personnel will complete all visit procedures per the SoA.

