Visit Interval Tolerance (days)		±3	_	±3		±3	±3	±3	±3	±3	±3	±3	±3	±3	±3	±3	±3	±3	b Visit 6 must not occur on the same day as Visit 5.
Visit Detail			F	Т			Т	F	Т	Т	Т	F	Т	Т	Т	F	Т	F	T = telehealth visit F = fasting visit
Review SMBG 6-point profiles			X															X	Review profiles collected in preceding week. See Section 8.1.1.1.
Paper Patient-Reported Ou	itcome	es																	
Treatment-Related Impact Measure - Diabetes (TRIM-D)			X															X c	c At Visit 18 or after, if a participant changes from the autoinjector to the prefilled pen, conduct this procedure on the day the change occurs.
Diabetes Injection Device Experience Questionnaire (DID-EQ)																		Х°	changes from the autoinjector to the prefilled pen, conduct this procedure on the day the change occurs.
Electronic Patient-Reporte	d Outo	comes																	
Diabetes Treatment Satisfaction Questionnaire - Status (DTSQ-s)			X																
Diabetes Treatment Satisfaction Questionnaire - Change (DTSQ-c)																		Х°	c At Visit 18 or after, if a participant changes from the autoinjector to the prefilled pen, conduct this procedure on the day the change occurs.
Simplicity of Diabetes Treatment Questionnaire (SIM-Q)																		Х°	c At Visit 18 or after, if a participant changes from the autoinjector to the prefilled pen, conduct this procedure on the day the change occurs.

Study I8H-MC-BDCW Table 1	& L	een ead- n								Trea	itmen	t							Comments
Visit Number	1	2	3	4	5	6	7	8	9	10	11	12	13	14	15	16	17	18	
Weeks from Randomization	-3	-2	0	1	1 a	2 b	3	4	5	6	7	8	9	10	11	12	14	16	a Visit 5 occurs 3 days after Visit 4 ± 1 day.
Visit Interval Tolerance (days)		±3	_	±3		±3	±3	±3	±3	±3	±3	±3	±3	±3	±3	±3	±3	±3	b Visit 6 must not occur on the same day as Visit 5.
Visit Detail			F	Т			Т	F	Т	Т	Т	F	Т	Т	Т	F	Т	F	T = telehealth visit F = fasting visit
Basal Insulin Experience Likelihood of incorporating into routine																		Х°	changes from the autoinjector to the prefilled pen, conduct this procedure on the day the change occurs.
Laboratory Tests and Samp	ole Co	llectio	ns																
Hematology	X		X													X			
Hemoglobin A1c (HbA1c)	X		X			X		X				X				X		X	
Clinical chemistry	X		X													X			
Glucose								X				X						X	
Lipid panel			X													X			
Urinalysis	X																		
Serum pregnancy	X		X																Collect for WOCBP only.

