### Overall design

#### **Blinding**

This is an open-label study. Investigators, participants, and study-site personnel will be unblinded to the assigned treatment. To eliminate potential biases, designated members of the Lilly study team will remain blinded throughout the study (see Section 6.3). Only a minimum number of Lilly personnel will see the randomization table and treatment assignments before the study is complete.

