#### **Blinding**

This is an open-label study. Investigators and participants will be unblinded to the assigned treatment groups.

The Lilly study team members who are closely involved in data interpretation and analysis planning will remain blinded throughout the course of the study. Only a minimum number of Lilly personnel will see the randomization table and treatment assignments before the study is complete.

The investigator should make every effort to preserve the blinding when contacting the Lilly study team members, including the Lilly clinical research physician or scientist.

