### Order of administering the questionnaires during the visit

If the participant is not adversely affected by their fasting condition, the questionnaires should be completed before the participant has discussed their medical condition or progress in the study with the investigator or study personnel.

Preferred administration order of these questionnaires is:

- 1. TRIM-D
- 2. DTSQ
- 3. SIM-Q
- 4. DID-EQ, and
- 5. Basal Insulin Experience: Likelihood of incorporating into routine.

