	Planned measurements at scheduled visits will be included.	scheduled visits will be included.
Laboratory values elevated or	Starts from the screening visit and	Starts after the day of first dose of
low, vital signs, and body weight	ends prior to or on the day of first	study treatment and ends at the last
categorical measures	dose of study treatment.	visit in the study including both
		treatment period and follow-up
	All available measurements at	period.
	scheduled and unscheduled visits	All available measurements at
	will be included. The baseline for	scheduled and unscheduled visits in
	the weight will be the last non-	the specified analysis period will be
	missing value during the baseline	included.
	period.	
Anti-LY3209590 antibody	Refer to PSAP.	Refer to PSAP.

Analysis	Baseline Observations	Postbaseline Observations
Patient-reported outcomes	The baseline will be the data	All scheduled visits after Visit 3
	collected at Visit 3.	• Last collection after Visit 3
		For sensitivity analysis to
		compare the treatment effect of
		LY3209590 with autoinjector
		and insulin glargine:
		o LY3209590: Last collection
		prior to or at the time of
		switch to prefilled pen
		
 
Glargine: Last collection
 

		after Visit 3

Abbreviations: ANCOVA = analysis of covariance; CRF = case report form; EAS1 = efficacy analysis set 1; EAS2 = efficacy analysis set 2; HbA1c = hemoglobin A1c; MMRM = mixed model repeated measurement; N/A = not applicable; TEAE = treatment-emergent adverse event.

All analyses will be implemented using SAS Enterprise Guide Version 7.1 or above.

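### The Visit 3 flow lists open-label randomisation before baseline procedures, so baseline TRIM-D could be answered with the arm known, which could bias the TRIM-D change from baseline

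*Protocol*

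**What the plan says.** **Order at Visit 3.** Protocol section 4.1 (Weeks 0-16) introduces the sequence with "This is the general flow for Visit 3". After the enrolment criteria are confirmed, "participants are randomly assigned to an intervention group". Next, "study personnel complete baseline procedures and sample collection". Dosing training and the first dose follow.

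**Blinding.** Section 4.2 states: "Investigators, participants, and study-site personnel will be unblinded to the assigned treatment". Section 6.3 repeats this for investigators and participants.

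**When the questionnaires are given.** SoA Table 1 schedules TRIM-D and DTSQ-s for the first time at Visit 3. The SAP (section 4.1, patient-reported outcomes row) takes as baseline the data "collected at Visit 3".

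**Timing rule within a visit.** Section 8.1.2 has one. Provided that fasting does not adversely affect the participant, "the questionnaires should be completed before the participant has discussed their medical condition or progress in the study with the investigator or study personnel". It does not mention randomisation or allocation. At Visit 3 the SoA ties the antibody and biomarker samples to a time before dosing, and asks that eligibility be confirmed before randomisation. It carries no such comment for the questionnaires.

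**Use of the baseline.** SAP 4.4.2.3.1 analyses TRIM-D scores and change from baseline with an MMRM like that of the other efficacy endpoints, and the last post-baseline value with an ANCOVA that includes baseline TRIM-D. SAP 4.4.2.3.2 summarises DTSQ-s at baseline and compares the arms there. SAP 4.4.2.3.3 tests DTSQ-c, a direct rating of change, by Wilcoxon rank sum with no baseline term.

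**The concern.** A baseline covariate is safe to adjust for because it cannot depend on treatment. That guarantee is lost if the participant knows the arm when answering. TRIM-D covers treatment burden, daily life and psychological health, which relief or disappointment at a weekly or daily assignment could plausibly colour. A site that follows the listed order would collect it at that point.

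TRIM-D change from baseline to Weeks 26 and 52 is a named secondary endpoint. If the arms differ at baseline because of the allocation itself, subtracting or adjusting for that baseline moves part of the difference into the estimated treatment effect. Nothing in the planned TRIM-D analyses separates the two.

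**Working it through.** **1. What the documents allow.** Set side by side:

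| Source | What it fixes for Visit 3 | Before allocation? |
|---|---|---|
| Protocol 4.1 | randomise, then baseline procedures | No; the listed order is the reverse |
| Protocol 8.1.2 | questionnaires before discussing condition or progress, if fasting is tolerated | Not stated |
| SoA Table 1 | TRIM-D and DTSQ-s at Visit 3, no order comment | Not stated |
| SAP 4.1 | Visit 3 data are the baseline | Not stated |

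No provision requires the questionnaires before randomisation.

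**2. Plan figures.** The only power figures are for HbA1c. With 284 per arm and SD 1.1, SE = 1.1 × √(2/284) = 0.0923.
- Margin 0.4: Φ(0.4/0.0923 − 1.96) = 99.1%.
- Margin 0.3, and likewise superiority at −0.3: Φ(0.3/0.0923 − 1.96) = 90.1%.
- Randomised: 284/0.85 = 334.1, so 335 per arm and 670 in total.

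These reproduce the plan. There is no counterpart for TRIM-D.

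**3. How a shift carries through.** Let the baseline difference caused by knowing the arm be s (SD units, LY3209590 minus glargine), the baseline to follow-up correlation be ρ, and the true effect be zero. Take equal variances.
- Raw change: bias = −s, SE = √(2(1−ρ)) × √(2/n).
- Baseline-adjusted: bias = −ρs, SE = √(1−ρ²) × √(2/n).
- Follow-up score without the baseline: bias from this source = 0, SE = √(2/n).

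The rejection rate under a true null is P(|Z + bias/SE| > 1.96). Both s and ρ are assumptions. With n = 284, √(2/284) = 0.0839.

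Worked case, s = 0.1 and ρ = 0.5: adjusted bias = −0.05; SE = 0.866 × 0.0839 = 0.0727; rejection rate 10.6%.

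| s | Adjusted bias, ρ = 0.3 / 0.5 / 0.7 | Rejection rate, adjusted | Rejection rate, raw change |
|---|---|---|---|
| 0 | 0 / 0 / 0 | 5% | 5% |
| 0.05 | −0.015 / −0.025 / −0.035 | 5.4% / 6.4% / 9.0% | 8.0% / 9.2% / 12.0% |
| 0.1 | −0.03 / −0.05 / −0.07 | 6.6% / 10.6% / 21.5% | 17.2% / 22.2% / 33.7% |
| 0.2 | −0.06 / −0.10 / −0.14 | 11.6% / 28.0% / 64.7% | 52.2% / 66.4% / 86.8% |

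The planned models are the adjusted ones. The raw-change column shows what baseline adjustment saves; it is not a planned test.

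**4. Would a shift be visible?** With 335 per arm, the SE of a baseline difference is √(2/335) = 0.0773 SD. A two-sided 5% baseline comparison would detect s = 0.2 about 74% of the time and s = 0.1 about 25% of the time. The SAP plans summary statistics for TRIM-D but no baseline test of it.

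**5. Cost of leaving the baseline out.** The SE rises by a factor 1/√(1−ρ²): 1.05, 1.15 and 1.40 for ρ = 0.3, 0.5 and 0.7.

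**The case against.** The strongest reply is that section 8.1.2 already settles the matter. It is the specific rule for questionnaires and should be read over a general flow. If confirming eligibility involves talking about the participant's condition, a site obeying 8.1.2 would hand out the questionnaires before that first step, and so before randomisation. The bullet on baseline procedures names no questionnaire, and TRIM-D is self-administered. The recall periods (two weeks for TRIM-D, the past few weeks for DTSQ-s) look back to the earlier treatment, which argues for a small shift. TRIM-D is ungated, and its later answers are given open-label in any case.

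Much of this stands. It is why the conclusion is that the baseline could be affected, with unknown size. But 8.1.2 is advisory, lapses if fasting troubles the participant (Visit 3 is a fasting visit) and is silent on allocation. The general flow is the only Visit 3 sequence that sites are given. A recall period limits the influence of present expectation without removing it.

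A reader might also infer three stronger things, which the documents do not support:
- **That DTSQ change is biased too.** DTSQ-s is never subtracted or used as a covariate, and DTSQ-c has no baseline term. Only the baseline DTSQ-s comparison is exposed.
- **That no later analysis could reveal or repair the problem.** A large shift would probably show in the baseline summaries, and a TRIM-D comparison without the baseline avoids this bias.
- **That the main result is at risk.** The primary and gated endpoint is HbA1c from the central laboratory.

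**Conclusion.** The gap is real and narrow. The written order permits baseline TRIM-D to be completed after the arm is known, and no provision prevents it. That could bias the TRIM-D change from baseline in the planned MMRM and ANCOVA. Whether it happens depends on site practice, and the documents give neither direction nor size. The percentages above rest on assumed values of s and ρ, equal variances and 284 per arm. They show that a modest shift would matter, not that one exists. No multiplicity-controlled error rate is involved, and the sample size and HbA1c power are unchanged. The change is worth making because it is almost free.

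**What to change.** **Protocol.** In section 4.1, reorder the Visit 3 flow: TRIM-D and DTSQ-s are completed, then randomisation is processed in IWRS, then training and first dose. In the SoA comments for both instruments at Visit 3 and in section 8.1.2, add: complete before randomization. Have the completion time written on the paper TRIM-D form so that it can be set against the IWRS randomisation time. A check of DTSQ-s time stamps alone would miss TRIM-D, because DTSQ-s is electronic and TRIM-D is on paper.

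**SAP.** The third version was approved before database lock, so many participants may already be past Visit 3; the documents do not give enrolment status. For them, add a sensitivity comparison of post-baseline TRIM-D scores that neither subtracts nor adjusts for the baseline. Report TRIM-D completion relative to randomisation wherever source records hold the time, and state the limitation where they do not.

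**Cost.** The protocol change needs one reordered list, two SoA comments, one sentence and one time field, with no added visit, assessment or sample. The sensitivity analysis is one extra model per score, with an SE about 5% to 40% larger for ρ from 0.3 to 0.7. It leaves untouched any effect of open-label answering at Weeks 26 and 52.

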#### Weeks 16-52 (Visits 18-33)

Participants assigned to LY3209590 will remain on their fixed dose according to the dosing instructions in Section 6.5.1.

During Weeks 16-52, if a participant is receiving the fixed dose of 400 U/week for at least 4 weeks and they have a median FBG >130 mg/dL for the previous week, the investigator should transition the participant to a prefilled pen, which will provide more dosing flexibility for higher doses. See Section 6.5.1 for details.

If a participant changes from the autoinjector to the prefilled pen, they will complete additional procedures per the SoA at the time of change and administer the first dose at the site.

#### Last study treatment visit: either Week 52 (Visit 33) or ED visit

Assessments for the transition to nonstudy diabetic treatment after the participant's last dose

The investigator will determine a participant's transition from study treatment to another nonstudy diabetic treatment (see Section 6.9).

Participants will continue their concomitant antihyperglycemic medications at the discretion of the investigator.

## Safety follow-up visits 801 and 802

Study personnel and participants complete all visit procedures described in the SoA.

The investigator will follow-up on the participant's transition from study treatment to another nonstudy diabetic treatment (see Section 6.9).

Participants will return study devices at the final study visit.

## 4.2. Scientific Rationale for Study Design

#### **Primary endpoint**

The primary efficacy measurement is HbA1c, a widely used measure of glycemic control that reflects a cumulative history of glucose levels in the preceding 2 to 3 months.

### Overall design

#### **Blinding**

This is an open-label study. Investigators, participants, and study-site personnel will be unblinded to the assigned treatment. To eliminate potential biases, designated members of the Lilly study team will remain blinded throughout the study (see Section 6.3). Only a minimum number of Lilly personnel will see the randomization table and treatment assignments before the study is complete.

#### Study duration

The treatment duration of 52 weeks is a reasonable time frame to observe the effects of LY3209590 as a fixed dose escalation compared to insulin glargine.

The follow-up visits after the last dose are designed to capture any additional safety signals and to monitor the transition from study treatment to nonstudy diabetic treatment.

#### **Comparator**

Insulin glargine was chosen as the comparator because it is a widely used basal insulin.

